14.17.4 Simulation

We evaluated type I error and power for each of the 8 possible groups under a variety of possible “truths” indicating various possible true underlying probabilities within each group.

14.17.4.1 Assumptions

Accrual – Two scenarios for the assumed two-year expected accrual are investigated: 1) 10 subjects per group and 2) 5 subjects per group. Note that these are averages, the actual number of available patients is simulated as a Poisson distribution with the specified mean. Also note that the group cap of 30 applies, and thus if the number of available patients in a group exceeds 30, only the first 30 available patients in that group will be enrolled in the study.

Dropouts – We assume no dropouts for the purpose of this simulation.

Control Rates – Table 14-17 shows the assumed control clinical benefit rates for each group.

Table 14-17 Assumed control CBR values used in the simulations.

Tumor Type	Assumed Control Rate (R_g)
Lung LSCL	0.45
Bladder	0.47
Breast	0.50
Colorectal	0.38
GIST	0.50
HNSCC	0.45
Ovarian	0.47
Sarcoma	0.40

We consider four possible scenarios, or possible “truths” in the simulation. These consisted of a null scenario (where the treatment has no effect for any group), an alternative scenario (where the treatment is effective in all groups), a scenario where the treatment was effective in two of the groups, and a scenario where the treatment was effective in half of the groups.

Treatment Rates - The treatment rates for each scenario are shown in the table below. Values identical to the control are shown in bold, while values greater than the assumed control rate are shown in italics.

	Null	Alternative	Two	Half
Lung LSCL	0.45	0.71	0.45	0.45
Bladder	0.47	0.73	0.47	0.47
Breast	0.50	0.75	0.50	0.50
Colorectal	0.38	0.65	0.38	0.38
GIST	0.50	0.75	0.50	0.75
HNSCC	0.45	0.71	0.45	0.71
Ovarian	0.47	0.73	0.73	0.73
Sarcoma	0.40	0.67	0.67	0.67

Simulation Details – For each scenario we simulated 1000 trials. For each interim within each trial, we ran 50,000 MCMC iterations after a 1,000 MCMC iteration burnin.

14.17.4.2 Results

A total of 8 scenarios were simulated (two accrual scenarios and four possible ‘truths’ for the clinical benefit rate). The probability of group success for each group is provided for each scenario in the below two tables.

Table 14-18 provides the probability of group success for each of the cohort – assuming expected accrual of 10 subjects/cohort and 5 subjects/cohort separately.

Table 14-18 Probability of group success

Two-year expected accrual: 10 subjects/cohort				
Group	Null	Alternative	Two	Half
Lung LSCL	0.158	0.915	0.208	0.305
Bladder	0.131	0.918	0.232	0.322
Breast	0.147	0.909	0.233	0.312
Colorectal	0.138	0.921	0.200	0.276
GIST	0.162	0.921	0.233	0.826
HNSCC	0.139	0.906	0.217	0.834
Ovarian	0.145	0.929	0.786	0.829
Sarcoma	0.135	0.939	0.758	0.852

Two-year expected accrual: 5 subjects/cohort				
Group	Null	Alternative	Two	Half
Lung LSCL	0.132	0.803	0.204	0.258
Bladder	0.140	0.830	0.196	0.265
Breast	0.160	0.807	0.232	0.261
Colorectal	0.135	0.794	0.194	0.278
GIST	0.155	0.826	0.212	0.688
HNSCC	0.140	0.820	0.190	0.657
Ovarian	0.151	0.819	0.587	0.652
Sarcoma	0.139	0.799	0.579	0.667

Entries in bold represent groups where the treatment effect is 0 (e.g. the treatment is ineffective). Thus, entries in bold are type I errors. Entries in italics appear where the treatment is effective, and thus indicate the power of the design.

Generally, type I error is controlled below 0.20 under the null scenario (the borrowing compensates for the multiple interim data reviews) and power is an increasing function of the expected sample size (power is higher in the higher accrual situation across treatment rate scenarios). In the alternative scenario there remains decently high probability of success even in the lower accruing situations. When fewer groups are effective in truth, the scenarios “half” and “two” are harder to discern. Note in any particular trial there should be a mix of high and low enrolling groups, thus some groups may enroll closer to 10 subjects while others may only enroll five. This would produce a power value somewhere between the two tables.

Power is reduced and type I error is inflated when the truth is a mixture of effective and ineffective treatment effects across the groups. Generally power is a function of the sample size.

Appendix 1 - Modeling Details

Recall at the first stage the groups are clustered according to a Dirichlet Process Mixture Model.

The number of clusters is not assumed to be known in advance but will instead be inferred from the data using Dirichlet Process Mixtures (DPM). The DPM looks across all the possible clusterings of the groups and assigns a probability to each based on the data. The prior distribution in a DPM is governed by a parameter α . When α is small, the prior favors large clusters. As α tends to zero, the prior tends to place all its mass on a single cluster containing all the groups. As α increases, the prior places more mass on clusterings with a large number of clusters. As α becomes very large, the prior places all of its mass on having a separate cluster for each group (that is, no borrowing across groups). Thus, by specifying extreme values of the prior one could force the groups into one cluster or force the groups to be analyzed in separate clusters. Here we choose a moderate version of $\alpha=2$ (common values might be anywhere between 0.5 and 5) and allow the data more control over the clustering.

The details of the prior are as follows. Let z_g represent the cluster to which group g belongs. Then $z_g \sim \text{Categorical}(\mathbf{p})$, where \mathbf{p} is the vector such that p_k is the probability that a group belongs to cluster k and $\sum_{k=1}^{\infty} p_k = 1$. We construct \mathbf{p} using a stick-breaking process:

$$p_k = \beta_k \prod_{i=1}^{k-1} (1 - \beta_i)$$

and

$$\beta_k \sim \text{Beta}(1, \alpha).$$

A large value of α thus removes a very small amount of probability for \mathbf{p} , resulting in many clusters, while a small value of α tends to produce probabilities near 1 for the first cluster.

Conditional on the clustering, we fit a hierarchical model which has an across groups distribution

$$\theta_g \sim N(\mu, \tau^2)$$

As discussed above, this across group distribution states that within a cluster we expect to see some variation in the parameters, with that variation governed by τ . When τ is small, there is minimal variation across groups within a cluster, and thus within the cluster the model would approach pooling. In contrast, when τ is large we expect large amount of across group variation, and thus even though the groups are in the same cluster the θ_g values may be quite different. Apriori we have no way of knowing τ , so we estimate it using the data combined with the prior distributions

$$\mu \sim N(0, 1.82)$$

and

$$\tau^2 \sim IG(3,0.5),$$

where $IG(\alpha, \beta)$ is the inverse gamma distribution defined by:

$$f(x|\alpha, \beta) = \frac{\beta^\alpha e^{-\beta/x}}{x^{\alpha+1} \Gamma(\alpha)}.$$

When the entire model is implemented (via Markov Chain Monte Carlo) we consider the full joint distribution of the clustering combined with the hierarchical model parameters. We average over the entire range of the uncertainty in the parameters to produce the posterior distribution for each group parameter θ_g , which is then used to drive the decisions in the model.

The primary efficacy variable, clinical benefit rate, will be analyzed by a Novartis designated Contract Research Organization (CRO), [REDACTED] Analysis details are provided in Appendix Q of the protocol, which is also included in Section 10 of this Report Analysis Plan (RAP).

[REDACTED]

All other data will be analyzed by a different Novartis-designated CRO, [REDACTED] [REDACTED] according to Section 10 of the study protocol which will be available in Appendix 16.1.1 of the Clinical Study Report (CSR). Important information is given in the following sections and details will be provided, as applicable, in Appendix 16.1.9 of the CSR. All statistical analyses will be performed using SAS® Version 9.3 (or higher).

2 Statistical and analytical plans

Data from all centers that participate in this protocol will be used. The analyses stated in this document will be based on all subjects' data upon data base lock. The study is early terminated by sponsor. Last subject's survival follow-up was closed on August 4, 2016.

All statistical analyses presented in this document are related to subject background information, efficacy, and safety variables collected for the study. All analyses are descriptive and no hypothesis testing is planned (except for the primary efficacy variable, which is described in Section 10). Data from all centers will be combined for any analysis. In general, there is no stratification factor being considered for the analysis with the exception of tumor type in the primary efficacy variable analyses. Missing data will not be imputed unless otherwise specified. All data collected in the study will be presented in the listings. In general, this document will detail the methods used in summaries/tabulations.

The study population consists of adult subjects with a diagnosis of a solid tumor or hematological malignancy that have been pre-identified as having ALK or ROS1 positive mutations, translocations, rearrangements or amplifications. Pre-identification of the mutation or activation in the pathway will be performed locally at a Clinical Laboratory Improvement Amendments (CLIA) certified laboratory prior to participation in the study. Subject must have archival or fresh tissue available for submission to a central laboratory selected by Novartis to allow for molecular testing related to pathway regulation. If the tissue is not available or is insufficient, the subject must be willing to undergo a fresh tumor biopsy to allow for this analysis. Mutation types from both local and central laboratories will be analyzed.

To be eligible for enrollment to this study, subjects must have received at least one prior treatment for their recurrent, metastatic and/or locally advanced disease and have no remaining standard therapy options anticipated to result in a durable response. Subjects must have progressive and measurable disease (per RECIST 1.1 or appropriate hematological response criteria) and are in need of treatment.

Subjects are administered with ceritinib at 750 mg once daily. A complete treatment cycle is defined as 28 days. Subjects may continue on study treatment until disease progression, withdrawal of consent, unacceptable toxicity, death, or any other reasons (e.g., physician's decision). After discontinuation of study treatment, subjects, regardless of reason for study treatment discontinuation will be followed for safety for 30 days after the last dose. Survival information will be collected every 3 months until 2 years after the last subject has enrolled in the study regardless of treatment discontinuation reason (except if consent is withdrawn). Additional survival assessments may be performed outside the 3 months follow-up schedules if a survival update is required for an interim assessment to meet safety or regulatory needs. Note that, survival follow-up has been terminated for this study on August 4, 2016.

The primary efficacy objectives of the study, clinical benefit (definition details see Section 6.1) associated with ceritinib treatment based on local investigator assessment, will be summarized. The clinical benefit rate will be analyzed using a Bayesian hierarchical model to evaluate trial success and futility, and the relationship between relevant pathway regulation and the response to treatment with ceritinib (if applicable). Analysis details are documented in Section 10.

Duration of response (DOR) based on local investigator assessment will be analyzed. In the event of a low response rate, DOR will be listed only without frequency summaries. Overall response (OR) will be summarized with the number and percentages of subjects for each response category (e.g., for solid tumor - CR, PR, SD, PD, Not evaluable). Progression-free survival (PFS) will be summarized using Kaplan-Meier (KM) methodology. Due to limited survival follow-up for the study, overall survival will only be descriptively summarized, ie, only the frequency of deaths will be provided.

Subject demographics, disease characteristics (including mutation analyses), ceritinib treatment, and safety variables will be summarized descriptively, by nominal visit (if applicable), and/or overall.

Data used for the analyses specified in this document will come from the Electronic Data Capture (EDC) system. In addition, the mutation data from the central laboratory will be collected in an Excel spreadsheet format and subsequently be uploaded to a secure FTP site by Novartis.

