The main purpose of this protocol amendment is to incorporate updates based on currently available safety data. Pancreatic enzyme elevations (lipase and/or amylase) occur in patients treated with ceritinib. Clinical data suggest that a small proportion (<1%) of patients treated with ceritinib can develop clinical pancreatitis, and the causal role of ceritinib in these cases cannot be excluded. Due to this finding, the protocol has been amended to include additional dose modification and follow up monitoring language for patients who may experience this safety finding.

Appendix Q “Bayesian Adaptive Design” was revised. In a single arm trial without a control arm, the quality of the inferences depend strongly on historical data used to create a credible estimate of the baseline control rate. For this and other trials within Novartis’s Modular phase II program, this required an estimate of the patient population that would be enrolled. A control estimate was initially formed for each group based on that population estimate. As enrollment progressed, a different patient population was enrolled in terms of previous line of therapy exposure (heavily pretreated). In order to produce the best inferences for future development decisions, it is important to change the assumed baseline control rates to match the population enrolled in the program, rather than relying on the pre-trial assumptions. Previously this section was tailored to the CLDK378AUS23 trial. The revised appendix will be used for all trials within Novartis’s Modular phase II program. The purpose of this section is to show how Bayesian adaptive design will be used for the analysis of the primary efficacy endpoint. Each trial will be analyzed according to the tumor cohorts that will be formed during the course of the study.

Additional changes include the possible discontinuation of survival follow-up if the primary endpoint of the study is not met, a revised definition for “End of Study” to clarify when data will be reported, and language modifications to maintain consistency with standard core protocol language for ceritinib clinical studies.

Changes to the protocol

Changes to specific sections of the protocol are shown in track changes using strike through red font for deletions and red underlined for insertions.

The following changes were implemented throughout the protocol:

List of study authors was updated.

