14.17 Appendix Q: Bayesian Adaptive Design

14.17.1 Introduction

This document outlines the adaptive design framework to be used for all trials within Novartis's Modular phase II program designed to link targeted therapy to patients with pathway activated tumors.

Although the selected tumor types may vary by trial, this document outlines the design and analysis approach based on 8 example tumor cohorts:

- Lung NSCL
- Bladder
- Breast
- Colorectal
- GIST
- HNSCC
- Ovarian
- Sarcoma

Other tumor types may be considered for trials if 1) 4 or more patients are enrolled in the cohort, and 2) a reasonable estimate of the clinical benefit rate is available.

The primary endpoint is clinical benefit rate (CBR) in each cohort, with clinical benefit being assessed at 16 weeks. All patients will receive the experimental treatment for that particular trial.

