10.4.1 Assumptions

Accrual - Table 1 shows the assumed two year expected accrual number as well as the assumed control rates for the 7 histologic groups (including “other”). Note these are averages, the actual number of available patients is simulated as a Poisson distribution with the specified mean. Also note that the group cap of 30 applies, and thus if the number of available patients in a group exceeds 30, only the first 30 available patients in that group will be enrolled in the study. Note given the low assumed enrollment rate for “other” (2), there is a high likelihood these subjects will not enroll sufficiently to enter the main analysis.

Dropouts – We assume no dropouts for the purpose of this simulation.

Control Rates – Table 1 also shows the assumed control rates.

Histology	Assumed 2 year accrual	Assumed Control Rate (R_g)
Breast	20	0.69
Colorectal	15	0.26
B-cell Lymphoma	6	0.60
Melanoma	8	0.30
ALCL	6	0.90
Ovarian	15	0.65
Other (where applicable)	2	0.50

Table 1 – Assumed 2 year accrual rates (accrual is simulated as a Poisson process with these means) and assumed control CBR values used in the simulations.

We consider four possible scenarios, or possible “truths” in the simulation. These consisted of a null scenario (where the treatment has no effect for any group), an alternative scenario (where the treatment is effective in all groups), a scenario where the treatment was effective in two of the groups, and a scenario where the treatment was effective in half of the groups.

Treatment Rates - The treatment rates for each scenario are shown in the table below. Values identical to the control are shown in bold, while values greater than the assumed control rate are shown in italics.

	Null	Alternative	Two	Half
Breast	0.69	0.88	0.88	0.69
Colorectal	0.26	0.50	0.26	0.50
B-cell Lymphoma	0.60	0.82	0.60	0.60
Melanoma	0.30	0.55	0.55	0.55
ALCL	0.90	0.97	0.90	0.90
Ovarian	0.65	0.85	0.65	0.85
Other (where applicable)	0.50	0.75	0.50	0.75

Simulation Details – For each scenario we simulated 1000 trials. For each interim within each trial, we ran 50,000 MCMC iterations after a 1,000 MCMC iteration burnin.

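### SAP Section 10 is not the protocol Appendix Q it claims to be: the control rates R_g differ in all three shared cohorts, and the final success threshold is 0.90 against 0.80

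*SAP*

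**What the plan says.** The SAP's introductory text, before Section 2, states: "Analysis details are provided in Appendix Q of the protocol, which is also included in Section 10 of this Report Analysis Plan (RAP". SAP Section 9 repeats this twice, equating the Appendix Q power table with SAP Table 2 and the Appendix Q accrual assumptions with Section 10.

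For the rates, SAP 10.4.1 says "Table 1 also shows the assumed control rates", and protocol 14.17.4.1 says "Table 14-17 shows the assumed control clinical benefit rates for each group". Both tables head the column R_g, the symbol in the decision rule Pr(π_g > R_g).

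The Amendment 1 rationale explains the history. Of Appendix Q it says "Previously this section was tailored to the CLDK378AUS23 trial". Because the patients enrolled were more heavily pretreated than expected, "it is important to change the assumed baseline control rates to match the population enrolled in the program, rather than relying on the pre-trial assumptions". It adds: "The revised appendix will be used for all trials within" the sponsor's modular program. The current appendix opens accordingly: "This document outlines the adaptive design framework to be used for all trials within" that program. It also says that "this document outlines the design and analysis approach based on 8 example tumor cohorts".

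SAP 2.1 lists the changes from the protocol's planned analyses. It mentions neither the control rates nor the threshold.

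**The concern.** Two texts that the SAP calls the same give different null values for the trial's only hypothesis tests. SAP Section 10 looks like the trial-specific appendix that Amendment 1 replaced. It names six histologic groups plus an Other group, and Section 9 cites a Table 4.2 of Appendix Q, a number the appendix no longer uses (its power table is now Table 14-18).

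If the amended rates are right, following the SAP hides real effects in breast and ovarian and raises false success in colorectal. If the SAP rates are right, an analyst who goes to Appendix Q, which the SAP names as the source, makes the opposite errors. The SAP was written after survival follow-up closed on August 4, 2016, and the clinical benefit analysis follows database lock. An open choice of R_g at that stage weakens pre-specification.

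The threshold adds a second problem. Protocol 10.8 justifies the sample size by Table 14-18, so it matters whether that table describes the 0.90 rule of protocol 10.4.

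**Working it through.** **1. The texts side by side**

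| Item | SAP Section 10 | Protocol Appendix Q |
|---|---|---|
| R_g breast | 0.69 | 0.50 |
| R_g ovarian | 0.65 | 0.47 |
| R_g colorectal | 0.26 | 0.38 |
| R_g B-cell lymphoma, melanoma, ALCL | 0.60, 0.30, 0.90 | none |
| Final success | > 0.90 (10.1.1, 10.3.3; also 6.1) | > 0.80 (14.17.1.1, 14.17.3.3) |
| Stated null error | at 0.10 | below 0.20 |

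Protocol 10.4.2 and 10.4.3 use 0.90. The interim cut-offs, minimum numbers, cap of 30 and priors are the same in both.

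**2. How far the null moves.** The model uses θ_g = logit(π_g) − logit(R_g). As odds ratios, the two nulls differ by:
- breast: (0.69/0.31)/(0.50/0.50) = 2.23
- ovarian: (0.65/0.35)/(0.47/0.53) = 2.09
- colorectal, in the other direction: (0.38/0.62)/(0.26/0.74) = 1.74

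The alternative in both documents is an odds ratio of about 3, for example (0.75/0.25)/(0.50/0.50) = 3.0 for breast in Appendix Q. On the log scale the null moves by about 73% (0.80/1.10), 67% (0.74/1.10) and 51% (0.56/1.10) of that effect.

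**3. Reproducing the documents' own tables.** The model was run as SAP 10.5 gives it: Dirichlet process mixture with α = 2 summed over all partitions; θ_g ~ N(μ, τ²) within a cluster; τ² ~ IG(3, 0.5); Poisson accrual over 104 weeks; response at 16 weeks; first look when 30 patients reach 16 weeks, then every 13 weeks. The prior μ ~ N(0, 1.82) was read both as variance 1.82 and as SD 1.82. The checks in this step use the SD reading.

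- SAP Table 2, Alternative, 0.90 rule, computed/stated: breast 0.910/0.924, colorectal 0.809/0.813, lymphoma 0.681/0.692, melanoma 0.703/0.698, ALCL 0.584/0.611, ovarian 0.845/0.839. Over all four scenarios the named groups agree within 0.05; the largest gaps are melanoma and breast in the Half scenario.
- Table 14-18 matches only at 0.80. There the model gives null 0.13–0.16 and alternative 0.92–0.94 (10 per cohort) or 0.79–0.82 (5 per cohort); the table states 0.13–0.16, 0.91–0.94 and 0.79–0.83. At 0.90 the model gives 0.05–0.07, 0.83–0.86 and 0.62–0.67.

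So these are two different simulated designs, and the power table behind protocol 10.8 does not describe the 0.90 rule.

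**4. One cohort on its own.** With no borrowing, θ ~ N(0, 1.82 + τ²) averaged over τ² ~ IG(3, 0.5), with a binomial likelihood at π = expit(θ + logit R_g). Pr(θ > 0 | data), variance reading:

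| Data | SAP R_g | Protocol R_g |
|---|---|---|
| Ovarian 4/5 | 0.75 | 0.90 (0.904) |
| Colorectal 3/5 | 0.91 | 0.80 |
| Breast 5/6 | 0.77 | 0.93 |
| Breast 8/10 | 0.78 | 0.97 |
| Ovarian 7/10 | 0.64 | 0.91 |
| Colorectal 5/10 | 0.92 | 0.75 |

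The 0.90 verdict changes in every row. It also changes for breast 13–16 of 20, ovarian 10–11 of 15 and colorectal 7–8 of 15. All these changes hold under both prior readings.

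**5. Full model, 0.90 rule.** Accrual is SAP Table 1 times the fraction shown, with 4000 trials per case (Monte Carlo SE at most 0.008). Groups without a protocol rate are analysed at the SAP rate. Ranges cover both prior readings. In (b) they also cover two assumptions about those other groups: no effect (low end) and the SAP alternative (high end).

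| Truth and result | R_g used | Quarter | Half | Full |
|---|---|---|---|---|
| (a) Protocol null: colorectal false success | SAP | 0.09–0.11 | 0.14–0.15 | 0.24–0.25 |
| | Protocol | 0.04–0.06 | 0.06–0.07 | 0.06 |
| (b) Protocol alternative: breast success | SAP | 0.17–0.26 | 0.23–0.31 | 0.32–0.41 |
| | Protocol | 0.43–0.53 | 0.67–0.76 | 0.89–0.93 |
| (b) Protocol alternative: ovarian success | SAP | 0.15–0.24 | 0.24–0.33 | 0.32–0.42 |
| | Protocol | 0.37–0.48 | 0.60–0.70 | 0.81–0.88 |
| (c) SAP null: breast false success | SAP | 0.06–0.09 | 0.08–0.09 | 0.10 |
| | Protocol | 0.26–0.30 | 0.42–0.43 | 0.65 |
| (c) SAP null: ovarian false success | SAP | 0.04–0.06 | 0.08–0.09 | 0.09 |
| | Protocol | 0.19–0.23 | 0.33–0.35 | 0.51–0.52 |
| (d) SAP alternative: colorectal success | SAP | 0.37–0.41 | 0.59–0.61 | 0.80–0.81 |
| | Protocol | 0.27–0.30 | 0.39–0.40 | 0.48–0.49 |

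Separately programmed runs of some cases differ by up to about 0.03 and do not change the picture. Taking each document as written, half accrual, case (c): breast false success is 0.62–0.63 under Appendix Q (its rates and 0.80) and 0.08–0.09 under the SAP.

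**The case against.** The strongest reply is that neither table was meant to fix the analysis value. Both captions describe values used in simulations, the Appendix Q cohorts are examples, and SAP 6.1 promises only a historical rate per tumor type. That is a fair reading. But the visible text gives no other values, and both tables use the symbol in the decision rule. If the tables do not set R_g, the primary null is not pre-specified at all, and the same repair is needed.

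Second, supersession is inferred. The pre-amendment appendix is not available, and Amendment 1 does not say that Table 14-17 holds this trial's re-estimated rates. Colorectal rises from 0.26 to 0.38, which heavier pretreatment does not obviously explain. This stands as a reason to justify each rate. It does not rescue the statement that the two texts are the same.

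Third, 0.90 is not an SAP departure: it agrees with protocol 10.4, and 0.80–0.90 is labelled promising in both. Correct; on the threshold the protocol contradicts itself.

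Fourth, the study ended early, it is signal-seeking, and no document shows that these cohorts reached the 3-patient minimum. Some small examples are also close to the line, and some very small cohorts show no reversal (ovarian at 4 patients, colorectal at 3). This limits what can be said about the actual result. The analysis is still planned, and cohorts of 5 to 10 can change verdict.

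**Conclusion.** The concern holds. The identity statements in the SAP are wrong, all three shared control rates differ, and the difference is undeclared. The rates change verdicts in cohorts as small as five patients. At half accrual they change breast and ovarian success by roughly 0.36 to 0.45 when the Appendix Q alternative is true, and roughly double colorectal false success when the Appendix Q null is true. The bias runs in both directions, so neither table is a harmless default.

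That the SAP rates are superseded is a well-supported inference, not a demonstrated fact. The exact sizes depend on the accrual fraction and on how the prior for μ is read. The textual conflict depends on neither.

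**What to change.** In the SAP:

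- State one R_g for each analysed cohort, with its source, and say that it is the value used in the decision rules. By default use the amended Appendix Q value where one exists; otherwise record and justify the departure in SAP 2.1.
- For analysed cohorts without a protocol rate (B-cell lymphoma, melanoma, ALCL, any added cohort), document a rate set without reference to that cohort's outcomes.
- Correct the identity statements in the introductory text and Section 9.
- Confirm that the 0.90 threshold of protocol 10.4 and the SAP applies, and reconcile the 0.80 in Appendix Q with it.
- Restate the operating characteristics for the rates and threshold actually used.
- Optionally, report each cohort's posterior under the other table as a sensitivity analysis.

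The cost is SAP wording, a short justification per rate and one re-run of the existing simulation. No new data are needed.
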